#### ***Change from baseline in HbA1c 26 weeks after randomisation (step 4)***

*As the fourth step of the hierarchical testing procedure superiority of HbA1c 26 weeks after randomisation with mealtime faster-acting insulin aspart compared to NovoRapid® is to be confirmed. The confidence interval from the primary analysis 1) will be used to determine superiority. Superiority will be confirmed if the upper boundary of the two-sided 95% confidence interval of the mean treatment difference (mealtime faster-acting insulin aspart minus mealtime NovoRapid®) is below 0%.*

#### ***Change from baseline in 1,5-Anhydroglucitol after 26 weeks of treatment after randomisation (step 5)***

*Step 5 in the hierarchical testing procedure is to confirm superiority of changes from baseline in 1,5-anhydroglucitol 26 weeks after randomisation with mealtime faster-acting insulin aspart compared to mealtime NovoRapid®.*

*The analysis for the primary 1,5-anhydroglucitol estimand will be done using all subjects included in FAS and using the in-trial observation period. The change from baseline in 1,5 anhydroglucitol will be analysed using a model similar to 1) except with the corresponding baseline value as covariates. Superiority will be confirmed if the upper boundary of the two-sided 95% confidence interval of the mean treatment difference (mealtime faster-acting insulin aspart minus mealtime NovoRapid®) is below 0%.*

~~Change from baseline in 1,5 anhydroglucitol after 26 weeks of treatment will be analysed based on all planned post-baseline measurements until or at 26 weeks using a MMRM for repeated measurements, similar to the model used for analysis of the primary endpoint except with baseline~~

~~1,5 anhydroglucitol as covariate. The superiority will be evaluated based on the comparison of mealtime faster acting insulin aspart and mealtime NovoRapid®.~~

~~The sensitivity of the analysis will be addressed using the pattern mixture models described in section 17.3. Only the sensitivity analyses 5) and 6) in section 17.3 will be applied excluding the analyses where the non-inferiority margin of 0.4% are added to subjects withdrawing in the faster acting insulin aspart arm.~~

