#### **8.5 Laboratory assessments**

Except for urine pregnancy testing, which will be performed locally, all laboratory analyses will be performed by a central laboratory contracted by Novo Nordisk. The central laboratory will provide

all laboratory supplies for the sampling and transportation of all blood and urine samples taken during the trial. The central laboratory may utilise subcontractors.

A detailed description of the procedures for obtaining the samples, handling, storage, and shipment of the samples are specified in a trial-specific laboratory manual provided to the sites by the central laboratory. Information regarding laboratory materials such as tubes and labels are also described.

Laboratory samples can be drawn on another day than on the day of the actual visit, as long as it is within the visit window, as stated in the flowchart in section [2](#).

If laboratory samples need to be retaken due to missing result(s) (e.g. haemolysed, sample leaked during transit, sample not being conclusive, lost in transit, etc.), the subject should be called in for resampling. Please see the laboratory manual for further guidance.

Only laboratory samples specified in the protocol should be send to the central laboratory for analysis; if additional laboratory sampling is needed, e.g. to follow up on AEs, this should be done at the local laboratory.

Samples will be coded in order to keep subject's identity anonymous.

Laboratory results will be made available by the central laboratory. The laboratory provides results to the trial sites in the units preferred by the trial sites while the results that are transferred to the trial database will always be in SI units.

Final laboratory reports must be reviewed, dated, and signed by the Investigator on the day of evaluation. It must be specified whether out of range results are clinically significant. Review of laboratory reports must be documented either on the documents and/or in the subject's medical record.

If any clinically significant abnormalities occur at screening (Visit 1) these must be recorded on the Concomitant Illness Form in the eCRF. Any clinically significant deterioration of a pre-existing condition as well as any new clinically significant signs or symptoms should be reported as an AE in accordance with section [12.2](#).

The Investigator will not be able to review the meal test and antibody results for AEs as the antibody samples will be analysed after LPLV.

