## **8.5.1      Laboratory assessments of efficacy**

### **8.5.1.1      1,5-anhydroglucitol**

Blood samples will be drawn to determine the level of 1,5-anhydroglucitol in order to evaluate post prandial glycaemic fluctuations.

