#### **2.4.1.2 Section 4.1.2 Secondary objectives**

To confirm *the effect efficacy* in terms of glycaemic control of treatment with postmeal faster-acting insulin aspart in combination with insulin degludec in adults with Type 1 Diabetes Mellitus.

To confirm superiority of mealtime faster-acting insulin aspart compared to mealtime NovoRapid® both in combination with insulin degludec in adults with Type 1 Diabetes Mellitus in terms of:

- Postprandial glucose regulation (meal test)
- ~~Postprandial glucose excursions (1,5-anhydroglucitol)~~ Overall glycaemic control ( $HbA_{1c}$ )
- ~~Overall glycaemic control ( $HbA_{1c}$ )~~ Postprandial glucose excursions (1,5-anhydroglucitol)

To compare other efficacy and safety endpoints across mealtime faster-acting insulin aspart, postmeal faster-acting insulin aspart and mealtime NovoRapid®, all in combination with insulin degludec in adults with Type 1 Diabetes Mellitus.

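### The step 5 superiority rule for 1,5-anhydroglucitol points the wrong way: it was carried over from HbA1c, where lower is better.

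*Protocol*

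**What the plan says.** Amendment 2 rewrites the confirmatory hierarchy. HbA1c superiority becomes step 4 and 1,5-anhydroglucitol superiority becomes step 5, the last step; both compare mealtime faster aspart with mealtime NovoRapid.

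- **Objective** (Section 4.1.2 as amended): "To confirm superiority of mealtime faster-acting insulin aspart compared to mealtime NovoRapid® both in combination with insulin degludec", listing postprandial excursions measured by 1,5-anhydroglucitol as one of three items.
- **What the marker is** (Section 8.5.1.1): "Blood samples will be drawn to determine the level of 1,5-anhydroglucitol in order to evaluate post prandial glycaemic fluctuations". No favourable direction is given there or elsewhere.
- **Model for step 5** (Section 17.4.1 as amended): the change from baseline "will be analysed using a model similar to 1) except with the corresponding baseline value as covariates", so the treatment effect is an absolute difference in change.
- **Decision rule for step 5**: superiority holds if the "upper boundary of the two-sided 95% confidence interval of the mean treatment difference (mealtime faster-acting insulin aspart minus mealtime NovoRapid®) is below 0", followed by a percent sign.
- **Decision rule for step 4 (HbA1c)**: "The confidence interval from the primary analysis 1) will be used to determine superiority", followed by the identical criterion, percent sign included.
- **Units** (Section 8.5): "results that are transferred to the trial database will always be in SI units".
- **Hierarchy** (Section 17 as amended, Estimands): a rejection counts only if every preceding null hypothesis was rejected in faster aspart's favour.

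**The concern.** The same inequality serves two markers that move in opposite directions. For HbA1c, and for the meal-test increment in step 3, a lower value is better, so requiring the upper limit to lie below zero is right. 1,5-anhydroglucitol is lost in the urine when glucose spills over, so it falls with large excursions and recovers when they are controlled. For this marker the rule requires the whole interval to lie on the unfavourable side.

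Step 5 is a confirmatory test under family-wise error control. Applied literally, it cannot in practice confirm the benefit named in the objective, and a significant deterioration would meet the criterion. If the error is noticed only after unblinding, reversing the inequality will look like a choice made with the results in view.

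**Working it through.** **1. Where the sentence comes from.** In the protocol of 10 July 2015, Section 17.4.1, 1,5-anhydroglucitol was step 4 and its rule named the comparison without a direction. HbA1c superiority was step 5 and carried the upper-limit-below-zero rule. Amendment 2 exchanged the two steps, and the HbA1c rule now stands under both. The direction for 1,5-anhydroglucitol is thus new in Amendment 2.

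**2. What the unit shows.** The analysis is of an untransformed change. Where the amendment wants a log scale and a ratio it says so, as for lipids and profile fluctuation. A blood concentration held in SI units has no percent scale here, so the percent sign is the HbA1c unit. Zero is the same threshold in any additive unit, so the sign of the inequality is the substantive error. The percent sign shows only that the rule was not adapted.

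**3. The plan's own power figures.** The protocol states power only for HbA1c non-inferiority. The inputs are a margin of 0.4, 333 per arm, one-sided 2.5%, and true differences of 0 (step 1) and 0.1 (step 2). The SD is read as 1.2, because struck and new digits run together in the text at hand. A two-group t-test gives:

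| Step | Distance from margin | Stated power | Recomputed |
|---|---|---|---|
| 1 | 0.4 | 99.0% | 99.02% |
| 2 | 0.4 − 0.1 = 0.3 | 89.6% | 89.64% |

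The stated figures reproduce. None exists for step 5.

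**4. Step 5, scale-free.** Suppose a correctly directed test has power p. The expected z-value is then z = z_p + 1.96, and the written rule passes with probability Φ(−1.96 − z).

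- p = 0.80: z = 0.84 + 1.96 = 2.80, and Φ(−4.76) = 9.6 × 10⁻⁷.
- p = 0.90: z = 1.28 + 1.96 = 3.24, and Φ(−5.20) = 9.9 × 10⁻⁸.

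**5. Step 5 at the planned size.** Let d be the true standardised difference, faster aspart minus NovoRapid, with positive meaning benefit. It is an assumption shown over a range, since the protocol gives no effect or SD for this marker. With n = 333 per arm, √(2/n) = 0.0775.

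- As written: P(upper limit < 0) = Φ(−1.96 − d/0.0775).
- Corrected: P(lower limit > 0) = 1 − Φ(1.96 − d/0.0775).

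| d | Superiority declared, as written | Superiority declared, corrected |
|---|---|---|
| −0.3 | 97.2% | about 0 |
| −0.25 | 89.7% | about 0 |
| −0.2 | 73.3% | about 0 |
| −0.1 | 25.2% | 0.06% |
| 0 | 2.5% | 2.5% |
| +0.1 | 0.06% | 25.2% |
| +0.2 | 2.8 × 10⁻⁶ | 73.3% |
| +0.25 | 1.1 × 10⁻⁷ | 89.7% |
| +0.3 | 2.8 × 10⁻⁹ | 97.2% |

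The amendment expects about 8% to stop treatment and half of these to leave the trial. At 4% loss, 333 × 0.96 ≈ 320 per arm, and the written rule gives 1.5 × 10⁻⁷ at d = +0.25 and 88.5% at d = −0.25. The picture does not change.

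All these probabilities are for step 5 taken on its own, that is, once the sequence has reached it.

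**The case against.** **The direction is not in the protocol.** This is correct. The sign error rests on a general property of the marker, not on a cited figure. The identical rule and the HbA1c unit can be seen in the text without that knowledge. If the sponsor used a reversed scale, the protocol would have to say so, and it does not.

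**The text already restricts rejections to those favouring faster aspart.** The hierarchy paragraph and the objective do make the intent plain, so a reader could refuse to call a deterioration superiority. That puts the decision rule in conflict with the intent; it does not repair the rule.

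**Step 5 is heavily gated.** This is also correct. Superiority must first be shown on the meal-test increment and on HbA1c, both correctly directed. A significant worsening of 1,5-anhydroglucitol alongside both is unlikely, so the harm-side probabilities are conditional and not chances for the trial as a whole. The planning assumption is a zero HbA1c difference for the mealtime arm. Under it, step 4 would pass in only about 2.5% of trials and step 5 would rarely be tested. The more realistic loss is on the benefit side: the setting in which step 5 is reached is the one in which a true gain in this marker is plausible, and the rule would then miss it.

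**A beneficial effect could still pass by chance.** It could, with probability below 2.5%, falling to practically nil for any useful effect.

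**A SAP may put it right.** A SAP may elaborate, but this is an explicit rule and not missing detail. If the SAP corrects it silently, the two documents conflict.

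**Conclusion.** The point holds. The step 5 criterion is the HbA1c criterion applied to a marker for which higher is better, and nothing in the protocol corrects it. If a correctly directed test had 80% to 90% power, the written rule would confirm a true benefit with probability between about 10⁻⁶ and 10⁻⁷. An equally large worsening would be declared superiority with 80% to 90% probability, given that step 5 is reached.

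This rests on two assumptions: that 1,5-anhydroglucitol rises as excursions lessen, and an effect size that the protocol does not supply. The conclusion about direction does not depend on the second.

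The damage is confined to the final confirmatory step. The primary analysis, steps 2 to 4 and their error control are unaffected. It must still be fixed, because it inverts a confirmatory claim.

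**What to change.** Replace the step 5 criterion in Section 17.4.1 as amended with wording to this effect: superiority is confirmed if the lower limit of the two-sided 95% confidence interval for the difference in change from baseline in 1,5-anhydroglucitol, mealtime faster aspart minus mealtime NovoRapid, is above 0 in the assay's concentration unit. State once, in the endpoint or assessment section, that a higher value means better control of excursions. Remove the percent sign, and carry the same rule into any SAP.

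This should be done by amendment, or at the latest in a SAP that names the correction, before database lock and unblinding. The cost is one or two sentences. Data collection, model, sample size and the order of the hierarchy stay as they are, and the one-sided error at no difference remains 2.5%.

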#### **Change from baseline in HbA1c after 26 weeks of treatment (step 5)**

~~Step 5 in the hierarchical testing procedure is to confirm superiority of HbA1c after 26 weeks of treatment with mealtime faster acting insulin aspart compared to NovoRapid®.~~

~~The statistical analysis will be identical to the primary analysis. Superiority will be confirmed if the upper boundary of the two-sided 95% confidence interval of the mean treatment difference (mealtime faster acting insulin aspart minus mealtime NovoRapid®) is below 0%.~~

~~The sensitivity of the analysis will be addressed using the pattern mixture models as described in section 17.3. Only the sensitivity analyses 5) and 6) in section 17.3 will be applied excluding the analyses where the non-inferiority margin of 0.4% are added to subjects withdrawing in the faster acting insulin aspart arm.~~

#### **2.29.4 Section 17.4.2 Supportive secondary endpoints**

*For all supportive secondary endpoints, meal-time faster-acting insulin aspart will be compared to meal-time NovoRapid®, and post-meal faster-acting insulin aspart will be compared to meal-time NovoRapid®, unless otherwise stated.*

##### **2.29.4.1 Section 17.4.2.1 Efficacy endpoints**

*All endpoints except insulin dose in this section will be assessed using the FAS and the in-trial observation period and repeated using the on-treatment observation period. Insulin dose will be presented using SAS and will therefore only use the on-treatment observation period.*

#### **Change from baseline in FPG after 26 weeks of treatment after randomisation**

*Change from baseline in FPG after 26 weeks of treatment after randomisation will be analysed based on all planned post-baseline measurements until or at 26 weeks using a model ~~an MMRM similar to 1) the model used of the primary endpoint~~, except with baseline FPG as covariate.*

**HbA1c responder after 26 weeks of treatment after randomisation:**

**HbA1c < 7.0%**

A dichotomous (responder/non-responder) endpoint will be defined based on whether a subject has met the ADA HbA1c target (HbA1c < 7.0%) ~~after 26 weeks of treatment after randomisation~~.

This responder endpoint will be analysed based on a logistic regression model using treatment, region and *bolus adjusting method* as factors, and baseline HbA1c as covariate. *In analysis of the in-trial data subjects without an HbA1c measurement at week 26 will be treated as non-responders. In the on-treatment observation period analysis both subjects who discontinue faster-acting insulin aspart/NovoRapid® or withdraw from trial is included as non-responders. Predicted values from the model used for the primary analysis will be used for all subjects with no HbA1c at the last visit.*

**HbA1c < 7.0% without severe hypoglycaemia**

A dichotomous (responder/non-responder) endpoint will be defined based on whether a subject has met the ADA HbA1c target (HbA1c < 7.0%) ~~after 26 weeks after randomisation of treatment without treatment emergent severe hypoglycaemic episodes. The withdrawals from their randomised treatment will be set to non responders. This is based on the assumption that the subjects would experience a severe hypoglycaemia after the withdrawal. A predicted value from the model used for the primary analysis will be used if a treatment completer does not have HbA1c at the last visit.~~

This responder endpoint will be analysed based on a logistic regression model using treatment, region and *bolus adjusting method* as factors and baseline HbA1c as covariate. *In analysis of the in-trial data subjects without an HbA1c measurement at week 26 will be treated as non-responders. In the on-treatment observation period analysis both subjects who discontinue faster-acting insulin aspart/NovoRapid® or withdraw from trial is included as non-responders.*

**HbA1c < 7.0% without severe hypoglycaemia and minimal weight gain (<3.0%)**

A dichotomous (responder/non-responder) endpoints will be defined based on whether a subject has met the ADA HbA1c target (HbA1c < 7.0%) ~~after 26 weeks of treatment after randomisation without treatment emergent severe hypoglycaemic episodes, and with minimal weight gain from baseline to 26 weeks of treatment after randomisation (defined as less than a 3% increase).~~

*This responder endpoint will be analysed based on a logistic regression model using treatment, region and *bolus adjusting method* as factors and baseline HbA1c and baseline body weight as covariates. In analysis of the in-trial data subjects without an HbA1c measurement at week 26 will be treated as non-responders. In the on-treatment observation period analysis both subjects who discontinue faster-acting insulin aspart/NovoRapid® or withdraw from trial is included as non-responders. The withdrawals from their randomised treatment will be set to non responders. This is*

~~based on the assumption that the subjects would experience a severe hypoglycaemia after the withdrawal. A predicted value from the MMRM model will be used if a treatment completer does not have HbA1c or body weight at the last visit.~~

~~This responder endpoint will be analysed based on a logistic regression model using treatment and region as factors and baseline HbA1c and baseline body weight as covariates.~~

**Change from baseline in 30- min, 1- hour, 2- hour, 3- hour and 4- hour PPG and in 30- min, 2- hour, 3- hour and 4- hour PPG increment ~~after 26 weeks of treatment~~ after randomisation (meal test)**

Laboratory measured PG from the meal test will be analysed for 30, 60, 120, 180, and 240 minutes PPG separately. The corresponding PPG increments will be derived separately using each PPG measurement minus the pre-prandial PG.

*Change from baseline in PPG and PPG increment endpoints 26 weeks after randomisation* ~~Change from baseline after 26 weeks of treatment in PPG and PPG increment endpoints~~ will be analysed separately using an ANOVA model including treatment, region and *bolus adjusting method* as factors, and the corresponding baseline value as covariate.

*Note as the meal test is only preformed once post baseline, subjects with no post baseline meal test will not contribute to the analysis.*

**Change from baseline in 7-9-7-point SMPG profile ~~after 26 weeks of treatment~~ after randomisation:**

In general, analyses will be based on the entire 7-9-7-point profile except for the analyses of nocturnal endpoints where information in the 9-point profile will be utilised. Duration of main meals and time of injection of bolus insulin, which will be collected in connection with 7-9-7 point profiles, will be summarised descriptively.

*PPG and PPG increments based on the 7-9-7-point profiles will be derived separately for PG measurements made 1 hour after a meal. In the following section this distinction will be considered implicit and without further explanation.*

*PPG will be recorded by the subjects as part of two 7-point and one 9-point SMPG profile prior to the visits. Individual mean mealtime PPG (post-breakfast, post-lunch, post-main evening meal) will be derived from the three profiles. Overall mean PPG will be derived from the individual derived mealtime PPG values.*

*PPG increment for each meal (breakfast, lunch, main evening meal) will be derived from the 7-point and 9-point profile as the difference between PPG values and the PG value before meal in*

*each separate profile. The mean of the derived increments will then be calculated separately for each meal. Mean 1 hour PPG increments over all meals will be derived as the mean of all corresponding mean meal increments.*

#### ***Change from baseline in mean of the 7-9-7-point profile***

The mean of the 7-9-7-point profile is defined as the area under the curve profile divided by the measurement time, and is calculated using the linear trapezoidal technique.

*Change from baseline in the mean of the 7-9-7-point profile 26 weeks after randomisation will be analysed using a model similar to 1) except with the corresponding baseline value as covariate. The mean of the 7-9-7 point profile will be analysed based on all planned post baseline measurements until or at 26 weeks using a MMRM similar to the model used for analysis of the primary endpoint and the corresponding baseline value as covariate.*

#### ***Change from baseline in mean PPG and PPG increment over all three meals***

*Change from baseline in mean PPG and PPG increment 26 weeks randomisation will be analysed separately using a model similar to 1), except with the corresponding baseline value as covariate.*

#### ***Change from baseline in individual meal (breakfast, lunch and main evening meal) PPG and PPG increment***

*Change from baseline in PPG and PPG increment endpoints 26 weeks after randomisation for the individual meals (breakfast, lunch, main evening meal) will be analysed separately using a model similar to 1) except with the corresponding baseline value as covariate.*

#### **PPG and PPG increment (mean, breakfast, lunch, main evening meal)**

~~PPG and PPG increments based on the 7-9-7 point profiles will be derived separately for PG measurements made at 1 hour. In the following section this distinction will be considered implicit and without further explanation.~~

~~PPG will be recorded by the patient as part of two 7-point and one 9-point SMPG profile prior to the visits. Individual mean mealtime PPG (post breakfast, post lunch, post main evening meal) will be derived from the three profiles. Overall mean PPG will be derived from the individual derived mealtime PPG values.~~

~~PPG increment for each meal (breakfast, lunch, main evening meal) will be derived from the 7-point and 9-point profile as the difference between PPG values and the PG value before meal in each separate profile. The mean of the derived increments will then be calculated separately for~~

~~each meal. Mean 1 hour PPG increments over all meals will be derived as the mean of all corresponding mean meal increments.~~

~~Change from baseline in PPG and PPG increment endpoints (mean and each separate meal) will be analysed based on all planned post baseline measurements until or at 26 weeks using a MMRM similar to the model used for analysis of the primary endpoint and the corresponding baseline value as covariate.~~

